## PATIENTS

This study includes two groups of patients:

**Group (A):** All patients with operable breast cancer , admitted and managed at the Surgical Oncology unit, Alexandria Faculty of Medicine, between Jan.2010 to Dec.2015, their data are retrospectively reviewed and analyzed.

**Group (B):** All patients with operable multifocal breast cancer excluding those indicated for neoadjuvant therapy and those diagnosed as inflammatory breast cancer admitted between May.2017 to May.2018 will be offered oncoplastic breast conserving surgery and prospectively evaluated for 24 months as regards the outcomes of using different oncoplastic techniques to extend the clinical utility of BCT as a surgical management for multifocal breast cancer.

[name]

الدكتور

[name]

الدكتور

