Furthermore, Multifocal/MC disease has also been implicated as a prognostic factor. Studies have demonstrated that MF/MC cancers may have an increased susceptibility to axillary lymph node (LN) involvement. It is unclear whether this is due to inaccurate staging by using the largest tumor dimension or if these malignancies have an inherent biologic capacity to spread.

In addition, MF/MC disease has been found to correlate with known risk factors suggesting an aggressive biology such as young age, higher grade, negative hormone receptor status, negative HER-2 status, and lymphovascular invasion. Yet the impact on outcomes is unclear with studies demonstrating mixed results.

Unfortunately, due to the relatively heterogeneous cohort of patients with MF/MC breast cancer, standardized guidelines are not well established.

Therefore, it remains unclear whether MF/MC breast cancers should be considered a separate category with a potentially unfavourable impact on prognosis and whether these lesions require specific treatment with more extensive surgery or committed adjuvant therapies.

[name]

[figure not shown]
✓

✓

✓

The present study is directed to analyze, in a large retrospective series of breast cancer patients treated at a single institution, the impact of (MF) breast cancers on the long-term survival in relation to other known pathological and clinical factors and to the type of treatment received. Furthermore, the prospective limb of this study is directed to evaluate the outcomes of oncoplastic techniques as a surgical management for multifocal breast cancer.

[name]

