## METHODS

**For group (A) patients The following data of will be included and recorded:**

- Age at diagnosis: young patients are defined as younger than 35 years.
- Surgery performed:
  - a-Breast conservation: involves lumpectomy with oncologically appropriate safety margins with either sentinel lymph node detection or axillary lymph node dissection according to the triple assessment of the patients. The introduction of different oncoplastic procedures in breast cancer surgery allows more breast conservation.
  - b-Mastectomy: modified radical mastectomy.
- Tumor characteristics: size, nodal status, presence of lympho-vascular invasion, amount of intraductal component, tumor grade, margin status, hormone receptor, and Her2 neu status(if available).
- Pathological determination of multifocal and unifocal tumors.
- The follow-up period of the patients was registered.
- The occurrence of loco-regional recurrence or distant metastases during the follow-up period was recorded and considered as an end point for follow-up.

Local recurrence is defined as recurrence in the original tumor bed (for BCS) or field of mastectomy.

Regional recurrence refers to metastatic disease in the ipsilateral axilla or supraclavicular lymph nodes or ipsilateral involvement of internal mammary nodes.

Loco-regional recurrence-free survival of patients who are pathologically multi-focal and uni-focal will be estimated using the Kaplan-Meier method and compared among different categories using log-rank tests (univariable analysis

in 4/12

([name])

of risk factors for loco-regional recurrence among multi-focal and uni-focal breast cancer patients).

Distal recurrence-free survival for both groups will be analyzed using the same test (univariable analysis of risk factors for distal recurrence).

Associations with local recurrence in uni-focal and multi-focal breast cancer patients are further evaluated using multivariable Cox proportional hazards regression model and summarized with hazard ratios 95 % confidence intervals (CIs).

Associations with distal recurrence uni-focal and multi-focal breast cancer patients will be further evaluated using multivariable Cox regression model.

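### Group A has no stated exclusion for neoadjuvant-treated or inflammatory cases and records neither feature, so its multifocal-versus-unifocal contrasts can be confounded and cannot be adjusted or checked for them

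*Protocol*

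**What the plan says.** The protocol's Patients section defines the retrospective cohort, Group A, as "All patients with operable breast cancer , admitted and managed at the Surgical Oncology unit, Alexandria Faculty of Medicine, between Jan.2010 to Dec.2015". No exclusion follows. The prospective Group B also starts from operable disease, limited to multifocal cancer, and is then narrowed by "excluding those indicated for neoadjuvant therapy and those diagnosed as inflammatory breast cancer".

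For Group A, the Methods section lists age, the operation performed, tumour and pathology items, focality, follow-up and recurrence.
- The tumour items are "Tumor characteristics: size, nodal status, presence of lympho-vascular invasion, amount of intraductal component, tumor grade, margin status", followed by hormone receptor and, where available, HER2 status.
- The only treatment item is the operation: breast conservation or "Mastectomy: modified radical mastectomy".
- Focality comes from "Pathological determination of multifocal and unifocal tumors", with no rule for specimens removed after neoadjuvant therapy.

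The Introduction says the retrospective series will study multifocality "in relation to other known pathological and clinical factors and to the type of treatment received". It also names better neoadjuvant chemotherapy, with complete or near-complete remission or much smaller disease extent, as one reason the traditional preference for mastectomy may change.

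For analysis, the protocol plans log-rank tests and multivariable Cox models for local and distal recurrence, with no covariate list. The SAP lists chi-square, Fisher's exact and Monte Carlo tests only. Neither document plans an adjusted model for the choice of operation.

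**The concern.** Neoadjuvant therapy and inflammatory presentation can each bear on the operation chosen and on the risk of recurrence. If either is more common in one focality group, a crude MF-versus-UF difference in mastectomy use or recurrence can arise with no effect of focality at all.

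A second problem is separate from confounding. Focality is read from the surgical specimen. If treatment clears secondary foci first, a tumour that was multifocal at diagnosis can be recorded as unifocal.

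At stake are the Group A secondary objectives: MF and mastectomy (Objective 2), factors for breast conservation in MF disease (3), local relapse after conservation (4), and survival and loco-regional relapse (5), together with the distal recurrence analysis in Methods. Objective 6, the management recommendations, would draw on these results. No comparison of Group A with Group B is needed for the problem to arise, because it lies inside Group A.

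**Working it through.** The documents give no sample size, event count, effect size or share of neoadjuvant or inflammatory cases. There is no planned figure to reproduce.

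**1. Does Group A contain these patients?** Both groups are described as operable, and Group B then removes neoadjuvant-indicated and inflammatory cases. If operable already excluded them, that clause would be redundant. The natural reading is that Group A can include them. This is an inference, because operable is not defined.

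**2. Could the listed data identify them?** No. None of the Group A items records systemic treatment before surgery or inflammatory presentation. Pathological size and nodal status are weak substitutes, because neoadjuvant therapy can change them before they are measured.

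**3. Could the planned analyses allow for them?** The Cox models cannot include variables that are not collected. Mastectomy use has no adjusted model in either document.

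**4. Illustration for mastectomy use.** Every input here is an assumption. Let s be the share of affected patients (neoadjuvant or inflammatory), m the mastectomy risk in affected patients, and 50% the risk in the others. Both risks are the same in MF and UF, so there is no true MF effect.

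Crude risk: P = 0.50 + s(m − 0.50). Crude OR = [P_MF/(1 − P_MF)] / [P_UF/(1 − P_UF)].

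The first six rows take s at 20-30% in MF and 10-15% in UF, with m at 85-90%. The next two set m at 40%. The last gives both groups the same share.

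| s in MF | s in UF | m | P_MF | P_UF | Crude OR |
|---|---|---|---|---|---|
| 20% | 15% | 85% | 0.570 | 0.5525 | 1.07 |
| 20% | 10% | 85% | 0.570 | 0.535 | 1.15 |
| 20% | 10% | 90% | 0.580 | 0.540 | 1.18 |
| 30% | 15% | 85% | 0.605 | 0.5525 | 1.24 |
| 30% | 15% | 90% | 0.620 | 0.560 | 1.28 |
| 30% | 10% | 90% | 0.620 | 0.540 | 1.39 |
| 20% | 10% | 40% | 0.480 | 0.490 | 0.96 |
| 30% | 15% | 40% | 0.470 | 0.485 | 0.94 |
| equal | equal | any | equal | equal | 1.00 |

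The first and sixth rows are the extremes of the 85-90% scenario: 0.570/0.430 = 1.326 against 0.5525/0.4475 = 1.235 gives 1.07, and 0.620/0.380 = 1.632 against 0.540/0.460 = 1.174 gives 1.39.

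**5. Illustration for recurrence.** Let RR be the assumed recurrence risk ratio for affected versus other patients, again with no true MF effect.

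Spurious MF:UF ratio = [1 + s_MF(RR − 1)] / [1 + s_UF(RR − 1)].

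| s in MF / s in UF | RR 1.5 | RR 2 | RR 3 |
|---|---|---|---|
| 10% / 10% | 1.00 | 1.00 | 1.00 |
| 20% / 10% | 1.05 | 1.09 | 1.17 |
| 30% / 10% | 1.10 | 1.18 | 1.33 |
| 40% / 20% | 1.09 | 1.17 | 1.29 |

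For example, with 30% / 10% and RR 3: (1 + 0.30 × 2)/(1 + 0.10 × 2) = 1.60/1.20 = 1.33.

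These tables cover confounding only. Misclassification of focality is not quantified, because the documents give nothing from which to set a rate.

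**The case against.** The strongest reply has four parts.

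*No bias has been shown.* This stands as a limit. The documents do not say how many Group A patients had either feature, nor that their share differs by focality. A reader might infer that the Group A results are confounded; the text supports only that they can be. A reader might also infer that no adjustment of any kind is possible. That goes too far: Cox models are planned for recurrence, and size, nodes, grade and receptor status are recorded. What is missing is direct adjustment for these two features.

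*The direction is a guess.* This stands too. It is tempting to assume that affected patients mostly had mastectomy, which would inflate the MF-mastectomy association. The Introduction presents neoadjuvant chemotherapy as something that may make mastectomy less necessary, and the 40% rows above reverse the bias. Clearing foci before pathology would also move treated patients from MF to UF, against the assumed excess in MF.

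*Objective 2 is descriptive, and neoadjuvant therapy may be on the pathway.* If multifocality itself prompts neoadjuvant therapy, adjusting for it answers a different question from the crude association. For the same reason, confining the main analyses to patients without it would be debatable. It would also remove an obvious candidate factor from Objective 3. This argues against making restriction the primary analysis. It does not argue against recording the variables.

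*The two groups need not match.* This is fair. No comparison of A with B is planned, and a retrospective cohort of all comers may properly be broader than a prospective surgical series. But the point rests on contrasts within Group A, so this reply does not meet it.

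**Conclusion.** The point holds as a gap in the plan for Group A. Inclusion of neoadjuvant-treated and inflammatory cases is the natural reading of the eligibility text, neither feature is on the data list, and the promise to relate outcome to treatment received cannot be kept for neoadjuvant therapy. Followed as written, the plan leaves the MF-versus-UF contrasts open to confounding and to misclassified focality, and nobody could tell from the data whether the effect is nil or material.

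Size and direction are unknown. The illustrative mastectomy odds ratios (about 1.07 to 1.39, or 0.94 to 0.96, or 1.00) and recurrence ratios (1.05 to 1.33 with unequal shares, 1.00 with equal shares) rest wholly on assumed inputs. They show that a modest spurious association is possible, not that one exists.

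Only secondary objectives are touched. The primary objective concerns oncoplastic surgery in Group B, where these patients are excluded, and it is not affected. The change is worth making because it is cheap, but the gap does not undermine the study's main question.

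**What to change.** 1. Add two items to the Group A data sheet: neoadjuvant therapy received (yes/no) and inflammatory disease (yes/no). Report their frequency by focality and by operation.
2. Name both as covariates or strata in the Cox models for local and distal recurrence.
3. Add an adjusted analysis of mastectomy use for Objective 2, for example a logistic model with focality and both items, shown beside the crude association so that the two questions stay distinct.
4. Keep neoadjuvant therapy as a candidate factor in Objective 3.
5. Report a sensitivity analysis restricted to Group A patients with neither feature, matching the Group B criteria as nearly as charts allow (Group B excludes by indication; charts may show only receipt). This also addresses misclassified focality after treatment, which covariate adjustment does not.
6. Bring the SAP into line, since it now lists only contingency-table tests.

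The cost is two items abstracted from existing charts, a little more analysis, and fewer patients in the sensitivity analysis. No patient's treatment changes.

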## METHODS

**For group (A) patients The following data of will be included and recorded:**

- Age at diagnosis: young patients are defined as younger than 35 years.
- Surgery performed:
  - a-Breast conservation: involves lumpectomy with oncologically appropriate safety margins with either sentinel lymph node detection or axillary lymph node dissection according to the triple assessment of the patients. The introduction of different oncoplastic procedures in breast cancer surgery allows more breast conservation.
  - b-Mastectomy: modified radical mastectomy.
- Tumor characteristics: size, nodal status, presence of lympho-vascular invasion, amount of intraductal component, tumor grade, margin status, hormone receptor, and Her2 neu status(if available).
- Pathological determination of multifocal and unifocal tumors.
- The follow-up period of the patients was registered.
- The occurrence of loco-regional recurrence or distant metastases during the follow-up period was recorded and considered as an end point for follow-up.

Local recurrence is defined as recurrence in the original tumor bed (for BCS) or field of mastectomy.

Regional recurrence refers to metastatic disease in the ipsilateral axilla or supraclavicular lymph nodes or ipsilateral involvement of internal mammary nodes.

Loco-regional recurrence-free survival of patients who are pathologically multi-focal and uni-focal will be estimated using the Kaplan-Meier method and compared among different categories using log-rank tests (univariable analysis

in 4/12

([name])

of risk factors for loco-regional recurrence among multi-focal and uni-focal breast cancer patients).

Distal recurrence-free survival for both groups will be analyzed using the same test (univariable analysis of risk factors for distal recurrence).

Associations with local recurrence in uni-focal and multi-focal breast cancer patients are further evaluated using multivariable Cox proportional hazards regression model and summarized with hazard ratios 95 % confidence intervals (CIs).

Associations with distal recurrence uni-focal and multi-focal breast cancer patients will be further evaluated using multivariable Cox regression model.

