## INTRODUCTION

Multifocal (MF) and multicentric (MC) breast cancers are relatively common clinical entities, with incidence in the literature ranging from 6% to 60%. This large variability is due to differences in definitions used, inclusion or exclusion of *in situ* disease, and methods of pathologic sampling. Most commonly, MF breast cancer typically refers to two or more synchronous areas of disease confined within the same quadrant versus MC disease, which refers to two synchronous areas of disease within different quadrants. Regardless of the definition, the tumor with the greatest diameter is typically used for staging purposes.

As advances in preoperative imaging continue, the number of MF and MC tumors identified increases, and better guidelines for their management are needed. In particular, questions still exist regarding the optimal loco-regional (LR) therapy for MF and MC breast cancer. Multifocality and multicentricity are regularly considered as a relative contraindication for breast-conservation therapy. The reasoning for this traditional paradigm is based on two assumptions. **Firstly**, the perceived higher risk for in-breast recurrence since it is assumed that in MF/MC cancer the risk of more invasive foci in the breast is greater, and therefore radiotherapy possibly less effective. **Secondly**, the expected less good cosmetic outcome due to wide excisions and larger boost volumes with more fibrosis. Consequently, the vast majority of patients with MF/MC, either clinically detected or visible on standard imaging (mammography, ultrasound) is advised to be treated with a mastectomy. However, such a tendency towards a more extensive surgery is debated. The COMICE trial did not show any reduction of local recurrence or any improvement of long-term survival in patients undergoing preoperative MRI.

Three more recent developments may change this traditional paradigm.

جامعة

**First**, the introduction of MRI has led to the identification of more small cancer foci besides the index cancer.

**Secondly**, more effective neo-adjuvant chemotherapy result in more complete or near complete remissions or substantial reductions in the extent of cancers. **Thirdly**, improved surgery by better localization techniques and oncoplastic procedures allow for more precise and complete breast conserving resections.

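### Group A pools six years without listing year of surgery or planning any adjustment for period, so the multifocality–surgery associations in secondary objectives 2 and 3 may be confounded by calendar time, to an unknown degree

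*Protocol*

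**What the plan says.** Protocol, PATIENTS: Group A is all operable breast cancer "admitted and managed at the Surgical Oncology unit, Alexandria Faculty of Medicine, between Jan.2010 to Dec.2015", reviewed retrospectively. That is six calendar years in one pool.

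Protocol, METHODS, Group (A): the list of data covers age, operation, tumor characteristics, focality, follow-up period and recurrence. The only time item is length of follow-up; year or date of surgery is not listed. Operation has two categories, "a-Breast conservation: involves lumpectomy with oncologically appropriate safety margins" and "b-Mastectomy: modified radical mastectomy". Under the first stands the remark "The introduction of different oncoplastic procedures in breast cancer surgery allows more breast conservation", but oncoplastic surgery is not a recorded value. Focality is by "Pathological determination of multifocal and unifocal tumors".

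Protocol, INTRODUCTION: "As advances in preoperative imaging continue, the number of MF and MC tumors identified increases". Among three recent developments it also lists that "improved surgery by better localization techniques and oncoplastic procedures allow for more precise and complete breast conserving resections".

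Protocol, Secondary objectives: objective 2 relates multifocality to use of mastectomy; objective 3 seeks the factors that go with conservation among multifocal patients.

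SAP, Analytical statistics: two qualitative variables are compared by chi-square, with Fisher's exact or Monte Carlo tests when expected counts are small. None of these adjusts for a third variable. The only multivariable models, the Cox models in the protocol's Group A methods, are for recurrence and not for choice of operation.

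**The concern.** For objective 2, multifocality is the exposure and the operation is the outcome. The protocol describes advancing practice as raising detection of the first and shifting the second towards conservation. If both happened within 2010–2015, later patients would be more often multifocal and less often treated by mastectomy, whatever the effect of multifocality on the surgeon's choice. A single pooled table would then understate the association of multifocality with mastectomy.

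Objective 3 works differently, because everyone in it is multifocal. There period may itself be a determinant of conservation, and it can lend a false association to any other factor whose frequency changed over the same years.

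At stake is how two secondary, observational objectives are read. The primary objective, which evaluates oncoplastic surgery, is not affected.

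**Working it through.** The documents give no sample size, effect size or yearly rate for objectives 2 and 3, so there is no planned figure to reproduce. The only input taken from the documents is the six-year window (Protocol, PATIENTS). Every trend below is an assumption, chosen to show a range.

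**Objective 2: set-up.** Six years of equal accrual. In year t the multifocal share is p and the mastectomy probability in unifocal patients is m, both moving linearly from year 1 to year 6. The within-year odds ratio (OR) for mastectomy, multifocal versus unifocal, is constant. The multifocal mastectomy probability is q = OR·m/(1−m) ÷ [1 + OR·m/(1−m)]. Summed over years:

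- A = Σ p·q (multifocal, mastectomy)
- B = Σ p·(1−q) (multifocal, conserved)
- C = Σ (1−p)·m (unifocal, mastectomy)
- D = Σ (1−p)·(1−m) (unifocal, conserved)

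The pooled OR, which the unadjusted table shows, is A·D/(B·C).

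**Worked case.** p = 0.10, 0.12, 0.14, 0.16, 0.18, 0.20; m = 0.80, 0.74, 0.68, 0.62, 0.56, 0.50; true OR 1.0, so q = m. Then A = 0.564, B = 0.336, C = 3.336, D = 1.764, and the pooled OR is (0.564 × 1.764)/(0.336 × 3.336) = 0.89.

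| Assumed trend | Multifocal share | Unifocal mastectomy | Pooled OR, true 1.0 | Pooled OR, true 2.0 |
|---|---|---|---|---|
| Mild | 10% to 15% | 75% to 60% | 0.96 | 1.92 |
| Middle | 10% to 20% | 80% to 50% | 0.89 | 1.73 |
| Strong | 8% to 24% | 85% to 45% | 0.79 | 1.51 |
| No exposure trend | 10% flat | 80% to 50% | 1.00 | 1.94 |
| No surgery trend | 10% to 20% | 65% flat | 1.00 | 2.00 |

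Two readings follow. First, both trends are needed: with either one absent, a true OR of 1.0 stays at 1.00. Second, the column for a true OR of 2.0 mixes two things. With no exposure trend it already pools to 1.945, which is non-collapsibility of the odds ratio and not confounding. Of the middle-case drop of 2.00 − 1.73 = 0.27, about 0.05 is of that kind. The column for a true OR of 1.0 is the cleaner measure of confounding.

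Under the same model, a Mantel-Haenszel estimate stratified by year, Σ(a·d)/Σ(b·c) with a, b, c, d the yearly cells, returns 1.00 and 2.00 in every row.

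**Objective 3: set-up.** Multifocal patients only. A factor has no within-year effect on conservation, but its frequency f drifts along with the conservation probability k. The pooled OR is [Σ f·k × Σ (1−f)(1−k)] ÷ [Σ f(1−k) × Σ (1−f)k].

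- f 30% to 50%, k 30% to 40%: (0.854 × 2.354)/(1.546 × 1.246) = 1.04
- f 20% to 60%, k 20% to 50%: (0.924 × 2.424)/(1.476 × 1.176) = 1.29
- f 20% to 60%, k 10% to 60%: (0.980 × 2.480)/(1.420 × 1.120) = 1.53
- f flat at 30%, k 20% to 50%: 1.00

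A factor that is stable over time is not distorted.

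**The case against.** The strongest reply is that the exposure trend is borrowed. The introduction speaks of tumors found by imaging, while Group A classifies focality at pathology, so better imaging need not raise the multifocal share recorded there. The introduction also describes the field and not this unit, and no start date is given for oncoplastic surgery. With either trend absent, objective 2 is not confounded by period. The larger shifts need multifocality to double or triple, and mastectomy to fall by 30 to 40 points, within six years. All of this stands. It limits the likely size and makes the confounding a possibility, not a finding.

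A reader might infer that the dataset is incapable of separating multifocality from year of treatment. The documents do not support that: patients are selected by admission date, so dates must exist in the source records. What is missing is a listed field and a planned adjustment.

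A reader might also infer that merging oncoplastic with standard conservation distorts objectives 2 and 3. It does not. Type of conservation is a subdivision of the outcome, so it cannot confound multifocality against mastectomy. Only conserved patients have a value for it, so it cannot predict conservation either.

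What the reply does not remove is that, without year in the analysis, the investigators could not show that the effect is small.

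**Conclusion.** The concern holds as a possibility of unknown size. Group A pools six years, year of surgery is not listed, and no analysis of choice of operation is adjusted. Objective 2 may be confounded by calendar period if multifocal share and use of mastectomy both moved during 2010–2015. Objective 3 may be confounded for factors that moved with conservation.

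Under the assumed linear trends and equal accrual, a true odds ratio of 1.0 in objective 2 becomes 0.96 with mild trends and 0.79 with strong ones. If share rises while mastectomy falls, the error is towards understating the link between multifocality and mastectomy. In objective 3 the assumed cases give false odds ratios between 1.04 and 1.53. None of these is an estimate for this unit. The change is worth making because it is cheap, and because it would show whether the problem exists.

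**What to change.** 1. Add year of surgery to the Group A data list, taken from the dates already needed to apply the 2010–2015 window.
2. Tabulate multifocal share and type of operation by period. If either is flat, confounding of objective 2 by period can be set aside.
3. In the SAP, stratify or adjust objective 2 by period, for example with a Mantel-Haenszel odds ratio or logistic regression, and report it beside the unadjusted result.
4. Include period as a candidate factor in objective 3, and adjust the other factors for it.

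The cost is one extra field at chart review, one table and one adjusted analysis. Because Group A is retrospective, the field can still be collected. The downside is sparse yearly strata, so two or three periods may be needed; wider periods leave some drift within each stratum unadjusted.

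Separately, recording standard versus oncoplastic conservation would be a useful descriptive item. It would help interpret objective 4 (local relapse after conservation), which now mixes two procedures, and it would show how often oncoplastic surgery was used in multifocal patients, which bears on the rationale for Group B. It is not a remedy for confounding in objectives 2 and 3.

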**Secondary objectives:**

1. Determine the burden of multifocal breast cancer among Egyptian population.
2. Determine to what extent the presence of (MF) is associated with the use of mastectomy.
3. Determine the factors that are associated with the use of BCT in the presence of (MF) disease.
4. Determine whether the presence of (MF) increased the rate of local relapse in patients treated with BCT.
5. Exploring the association between multifocality and overall survival and loco-regional relapse.
6. Stating a reliable recommendations for management of multifocal breast cancer.

Handwritten signatures and initials are present at the bottom of the page, including a signature in Arabic and a signature in English.

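### Group A recurrence curves lack event and censoring rules; if distant metastasis is censored, one minus Kaplan-Meier overstates the absolute risk of loco-regional recurrence as a first event

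*Protocol*

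**What the plan says.** In the Protocol, Methods, the list for Group (A) patients ends with this rule: "The occurrence of loco-regional recurrence or distant metastases during the follow-up period was recorded and considered as an end point for follow-up". The analysis follows directly: "Loco-regional recurrence-free survival of patients who are pathologically multi-focal and uni-focal will be estimated using the Kaplan-Meier method", and the curves are to be "compared among different categories using log-rank tests". Distant recurrence is handled separately: "Distal recurrence-free survival for both groups will be analyzed using the same test". The adjusted analysis is described as "Associations with local recurrence in uni-focal and multi-focal breast cancer patients are further evaluated using multivariable Cox proportional hazards regression model", with a parallel Cox model for distant recurrence.

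Two of the Secondary objectives depend on these analyses: "Determine whether the presence of (MF) increased the rate of local relapse in patients treated with BCT" and "Exploring the association between multifocality and overall survival and loco-regional relapse".

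The Methods define local and regional recurrence anatomically. They do not say which events end recurrence-free survival, which observations are censored, or what happens to a patient who dies without recurrence. Date of death is not among the Group A data items. The SAP (Data Management and Analysis) lists chi-square, Fisher and Monte Carlo tests only. It has no survival method, and neither document names a competing-risk method.

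**The concern.** Distant metastasis ends follow-up but has its own separate analysis. The natural inference is that a patient who metastasises first leaves the loco-regional curve as a censored observation, and that a patient with loco-regional recurrence leaves the distant curve in the same way. Kaplan-Meier treats a censored patient as someone who could still be observed to have the event later under the same hazard. Under this follow-up rule that patient cannot be. One minus the curve therefore does not estimate the share of patients whose first event is loco-regional. It is larger.

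The absolute figure matters because one objective is worded as a rate of local relapse after breast conservation, and another is to issue management recommendations. Readers will take the plotted percentages as the risk that patients faced.

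The silence on death is a second gap. The label recurrence-free survival can include death as an event or leave it out, and the two choices give different quantities.

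**Working it through.** **Inputs.** The documents give no recurrence, metastasis or death rate, no event count and no length of follow-up for Group A, so there is no stated figure to reproduce. All rates below are assumptions, shown over a range: a horizon of t = 5 years, constant cause-specific hazards, a loco-regional 1-KM of 8%, net distant metastasis risk of 15% to 40%, and net risk of death without recurrence of 5% to 10%.

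**Formulas.** A net risk R gives the hazard λ = −ln(1 − R)/t. With λ₁ loco-regional, λ₂ distant and λ₃ death, and Λ = λ₁ + λ₂ + λ₃:

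- 1-KM with competing events censored = 1 − exp(−λ₁t)
- first-event cumulative incidence = (λ₁/Λ) × [1 − exp(−Λt)]

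**Worked case, distant metastasis 15%, death left out.** λ₁t = −ln 0.92 = 0.0834 and λ₂t = −ln 0.85 = 0.1625, which sum to 0.2459. Incidence = (0.0834/0.2459) × (1 − 0.92 × 0.85) = 0.339 × 0.218 = 7.39%.

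| Net distant | Net death | 1-KM | Cumulative incidence | Excess, points | Excess, relative |
|---|---|---|---|---|---|
| 15% | not counted | 8.0% | 7.39% | 0.6 | 8% |
| 25% | not counted | 8.0% | 6.97% | 1.0 | 15% |
| 40% | not counted | 8.0% | 6.29% | 1.7 | 27% |
| 15% | 5% | 8.0% | 7.21% | 0.8 | 11% |
| 25% | 5% | 8.0% | 6.80% | 1.2 | 18% |
| 40% | 10% | 8.0% | 6.00% | 2.0 | 33% |

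The first three rows do not depend on how death is treated.

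**If death counts as an event instead.** The curve then measures loco-regional recurrence or death. With distant metastasis still censored and the same assumed net risks, 1-KM becomes 1 − 0.92 × 0.95 = 12.6% or 1 − 0.92 × 0.90 = 17.2%. The missing definition can therefore move the reported number further than the choice of estimator does.

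**Does the excess differ between groups?** At equal loco-regional hazard it grows with the competing risk. At a 1-KM of 10%, it is 0.5 points with a 10% competing risk and 1.6 points with 30%. When the loco-regional risks also differ, the ordering need not hold in absolute points: 10% loco-regional with 10% competing gives 0.50 points (5.3% relative), while 3% with 30% gives 0.47 points (18.8% relative).

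**Does the direction depend on the target?** Suppose the target is loco-regional recurrence at any time, including after metastasis. With a 1-KM of 10%, a distant risk of 20% and deaths ignored, the true any-time risk is 8.98%, 10.0%, 10.95% or 12.66% when the loco-regional hazard after metastasis is 0, 1, 2 or 4 times the hazard before it. The overstatement is therefore assured for first-event risk only.

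**The case against.** **The follow-up sentence may only name an outcome.** An end point for follow-up could mean something recorded during follow-up rather than the moment observation stops, and an overall survival objective needs observation past recurrence. This is a possible reading. It does not remove the gap, because the censoring rule is still unstated and the separate distant analysis still points to censoring at metastasis.

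**Death is not shown to be censored.** A reader might infer that ending follow-up at recurrence makes death a censoring event. The sentence does not mention death, and recurrence-free survival may count it as an event. The supported statement is that its handling is unspecified.

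**The group comparison is not shown to be biased.** A reader might infer that different competing risks invalidate the multifocal versus unifocal tests. They do not: log-rank and Cox with competing events censored compare cause-specific hazards, which is a legitimate question. The problem lies in the absolute percentages.

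**Which group has more distant disease is open.** The Introduction mentions possible greater nodal involvement and aggressive features in multifocal disease, but adds: "Yet the impact on outcomes is unclear with studies demonstrating mixed results". A larger distortion in the multifocal group is therefore conditional.

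**The effect may be small.** At 15% distant and 5% death it is 0.8 points. The top of the range needs 40% distant metastasis and 10% death at 5 years in patients described as operable, and nothing in the documents supports those rates. This stands, and it limits the weight of the point.

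**Gray's test could mislead.** With the same loco-regional hazard, cumulative incidence is 7.2% at the lower competing risks and 6.0% at the higher ones. A test on cumulative incidence could make the group with more metastasis look better on local relapse only because metastasis came first. This also stands, and it shapes the fix.

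**Conclusion.** The point holds in a limited form. The plan does not define the events or the censoring for loco-regional and distant recurrence-free survival, and it is silent on death. If distant metastasis is censored, as the text most naturally implies, 1-KM overstates the absolute risk of loco-regional recurrence as a first event. The excess is about 0.6 to 2 points on a 1-KM of 8%, under constant hazards and assumed 5-year competing risks that the documents neither give nor exclude.

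Three stronger conclusions should not be drawn: that death is censored, that the log-rank and Cox comparisons are invalid, or that the distortion is greater in multifocal disease. Nor is the overstatement established for loco-regional recurrence at any time, where stopping at metastasis can instead understate the risk. This is a worthwhile and inexpensive improvement to the reporting of absolute rates. Confidence is medium, because the event rule has to be inferred.

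**What to change.** In the Group (A) part of the Methods:

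1. State for each endpoint (local, loco-regional, distant) which events count, what is censored and when, and how death without recurrence is treated. The Kaplan-Meier text refers to loco-regional recurrence and the Cox text to local recurrence, so each needs its own rule.
2. Report Aalen-Johansen cumulative incidence of first loco-regional and of first distant recurrence, by multifocal or unifocal status, with 95% confidence intervals. Treat the other recurrence type and death without recurrence as competing events.
3. Keep log-rank and Cox as the group comparison and label the hazard ratios cause-specific. Do not use Gray's test as the main test of whether multifocality raises local relapse.
4. Abstract dates of death and, where records exist, loco-regional events after metastasis.

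**Cost.** A small amount of analysis outside SPSS 20, for which free software suffices, and slightly lower reported absolute rates. The overall survival objective already requires the death dates. Abstracting loco-regional events after metastasis is extra record review, limited to the patients who metastasised.
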